## 7. Data Management and Statistical Analysis Plan

### (1) Data Management

Original case report forms (CRFs), once data entry and verification are completed as required, shall be archived and saved in numerical order, and furnished with a retrieval catalog, etc., for inspection. Electronic data files, including databases, verification programs, analysis programs, analysis results, code books, and descriptive documents, should be classified and saved, with multiple backups stored on different disks or storage media, and properly preserved to prevent damage. All original records shall be preserved for the period stipulated by China's Good Clinical Practice (GCP).

### (2) Statistical Analysis

① General Principles: One-sided tests will be used for superiority tests, while two-sided tests will be used for other statistical tests. Quantitative indicators will be described using the number of cases, mean, standard deviation, median, minimum, and maximum. Categorical indicators will be described using the number of cases and percentages. All statistical analyses will be conducted using SPSS 26.0 statistical software.

#### ② Statistical Analysis Populations

**Full Analysis Set (FAS):** Refers to the ideal set of subjects that closely adheres to the intention-to-treat principle (including all randomized subjects who have received at least one treatment). This data set is formed by excluding randomized subjects using minimal and reasonable methods. For example, cases with no follow-up observation data after enrollment (no medication received) may be excluded. For the estimation of missing values for primary variables, such as case data where the entire treatment process was not observed, the last observation carried forward (LOCF, or "carry-forward") method will be used to impute missing trial data. The number of subjects evaluated for efficacy at the endpoint in each group will remain consistent with the number at the start of the trial.

**Per Protocol Set (PPS):** Includes all cases that comply with the trial treatment protocol, have good compliance (used the trial drug quantity between 80% and 120%), completed the required fields in the CRF, have measurable primary variables, have no missing baseline variables, and have no major violations of the trial protocol.

**Safety Analysis Set (SS):** Includes all enrolled cases that have used the study medication at

least once and have safety records after drug administration. This data set is used for safety analysis.

In this trial, baseline data will be analyzed using the FAS. Primary efficacy endpoints will be analyzed simultaneously on the FAS and PPS. Safety evaluation will be conducted using the SS.

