### **3.2 Research Methods**

#### **(1) Incidence and Severity of RIOM**

Guided by the principles of RCT, this study provides scientific research evidence to explore methods for improving the occurrence and severity of RIOM and enhancing the efficacy of CCRT. Specialized clinicians will observe whether patients develop RIOM and assess its severity during daily rounds, recording these in the progress notes. Grading will be performed using the WHO oral toxicity scale. The incidence and severity of RIOM will be statistically analyzed after the completion of concurrent chemoradiotherapy.

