## 6. Evaluation Indicators

- (1) Primary Evaluation Indicator: Incidence and severity of RIOM.
- (2) Secondary Evaluation Indicators: ①Duration of RIOM; ②Rate of completion of treatment measures; ③Adverse events classified according to CTCAE 5.0; ④Changes in BMI.

**Adverse Event (AE)** Any untoward medical occurrence in a subject during the clinical trial, which does not necessarily have a causal relationship with the treatment. An adverse event can be any unfavorable and unintended sign (including abnormal laboratory findings), symptom, or temporary illness associated with the use of the drug, whether or not related to the drug.

**Serious Adverse Event (SAE)** All serious adverse events occurring during the clinical trial must be recorded in the Serious Adverse Event (SAE) report. The occurrence of any of the following conditions should be considered a serious adverse event:

- ① Results in death;
- ② Is life-threatening;
- ③ Requires inpatient hospitalization or prolongation of existing hospitalization;
- ④ Results in persistent or significant disability/incapacity;
- ⑤ Results in a congenital anomaly or birth defect;
- ⑥ Other.

**Causality Assessment of Adverse Events** While recording in detail any abnormal symptoms, signs, laboratory tests, or other special examinations occurring during the clinical study, a causality assessment should be performed. According to the criteria for adverse reaction/event analysis, the causality assessment is classified as: 1-Definitely related; 2-Probably related; 3-Possibly related; 4-Probably unrelated; 5-Definitely unrelated.

- ① Is there a reasonable temporal relationship between the start of medication and the appearance of the suspected adverse reaction?
- ② Does the suspected adverse reaction fit the known adverse reaction profile of the drug? ③ Can the suspected adverse reaction be explained by the effects of concomitant medications, the patient's clinical condition, or other therapies?
- ④ Does the suspected adverse reaction disappear or alleviate after stopping or reducing the drug?
- ⑤ Does the same reaction reappear after re-exposure to the suspected drug?

Causality Determination Criteria: Determined sequentially according to the above indicators 1-5.

Causality Determination Table for Adverse Reactions					
Judgment Result	Assessment Indicators				
	①	②	③	④	⑤
Definitely Related	+	+	-	+	+

Probably Related	+	+	-	+	?
Possibly Related	+	+	+	±	?
Probably Unrelated	+	-	±	±	?
Definitely Unrelated	-	-	+	-	-

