### **III. Study Participant Recruitment**

#### **1. Inclusion Criteria**

- (1) stage III-IVa NPC (AJCC 8th edition) diagnosed via pathology in a tertiary hospital;
- (2) no previous radiotherapy, chemotherapy, surgery, immunization, or targeted therapy;
- (3) Karnofsky Performance Status score  $\geq 80$ ;
- (4) intact and normal oral mucosa before treatment;
- (5) age 18–75 years;
- (6) voluntary participation and provision of informed consent in person;
- (7) routine blood examination: white blood cell count  $\geq 4.0 \times 10^9/L$ , hemoglobin  $\geq 100g/L$ , neutrophil count  $\geq 1.5 \times 10^9/L$ , and platelet count  $\geq 100 \times 10^9/L$ ;
- (8) biochemical examination: total bilirubin  $\leq 1.5 \times$  the upper limit of the normal range (ULN), alanine aminotransferase and aspartate aminotransferase  $\leq 2 \times$  ULN, and estimated glomerular filtration rate  $\geq 60$  mL/min.

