### **3.2 Subject initiated withdrawal**

In accordance with the informed consent form, the subject has the right to withdraw from the trial midway. A subject is also considered "withdrawn" if they do not explicitly request to withdraw but are lost to follow-up by no longer receiving medication and testing. The reason for withdrawal should be ascertained and recorded whenever possible. Examples include: feeling the treatment is ineffective; finding certain adverse reactions intolerable; having commitments preventing continuation of the clinical study; economic factors; or being lost to follow-up without stating a reason. Regardless of the reason, the case report form for the withdrawn patient should be retained.

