### **3.3 Handling of Dropouts**

When a patient drops out, the investigator must fill in the reason for dropout in the CRF. They should contact the patient whenever possible, complete all feasible assessment items, and fill in the end-of-treatment follow-up record form, recording the time of the last dose if possible. For dropouts due to an adverse event that is ultimately judged to be related to the study drug following follow-up, this must be recorded in the CRF and the sponsor notified. No replacement cases are needed for dropouts.

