### **3.4 Criteria for Case Exclusion**

- ① Case selection does not meet the inclusion criteria;
- ② The trial medication was never used;
- ③ No data exists after randomization or major indicators are missing, or the data is obviously incomplete;
- ④ Use of medications prohibited by the trial protocol, making efficacy evaluation impossible.

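### LOCF in the FAS scores a patient lost before mucositis onset as RIOM-free: a small error if early loss is balanced, one that can favour either drug if it is not

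*Protocol*

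**What the plan says.** The FAS paragraph of Protocol II.7 (2) ② sets the rule for missing values of primary variables: "such as case data where the entire treatment process was not observed, the last observation carried forward". It adds that the number evaluated for efficacy at the endpoint in each arm "will remain consistent with the number at the start of the trial". The primary endpoint is analysed on the FAS and the per-protocol set (PPS) together.

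These other places bear on it:

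- II.6 names the endpoint: "Primary Evaluation Indicator: Incidence and severity of RIOM".
- II.3.2 (1) has clinicians grade RIOM at daily rounds on the WHO scale, and says: "The incidence and severity of RIOM will be statistically analyzed after the completion of concurrent chemoradiotherapy".
- III.1 (4) requires "intact and normal oral mucosa before treatment".
- III.3.2 gives among its examples of reasons for withdrawal: "feeling the treatment is ineffective; finding certain adverse reactions intolerable".
- III.3.3 asks the investigator, at dropout, to "complete all feasible assessment items".
- III.3.4 ③ lists as a ground for case exclusion: "No data exists after randomization or major indicators are missing, or the data is obviously incomplete". It does not say which analysis set this governs.

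**The concern.** RIOM is absent at entry by design and develops during six to seven weeks of radiotherapy. LOCF assumes that the last grade seen would have stayed the same. For a patient who leaves before onset that grade is 0, so the rule records no RIOM in someone who, on the protocol's own background figure, would more likely than not have developed it. Incidence is unaffected in patients lost after onset.

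Severity is affected too, but the effect cannot be determined because neither II.3.2 (1) nor II.6 says which grade counts. If it is the worst grade, a patient lost between onset and peak is graded too low. If it is the grade at the end of treatment, a patient lost near the peak may be graded too high.

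This is a non-inferiority trial, so it matters which way the error runs. Balanced early loss pulls any true difference towards zero, which slightly favours a non-inferiority claim when Sapylin is worse. Unequal early loss makes the arm with more early leavers look better. The two arms receive different drugs and III.3.2 expects withdrawal for intolerable reactions, so equal loss cannot be presumed. The protocol does not indicate which arm would lose more.

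III.3.4 ③ and ④ could also remove patients whom II.7 (2) ② would impute, so two analysts could build different full analysis sets.

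**Working it through.** **The plan's own figure.** II.3.3 (2) inflates 81 per arm for 10% loss: 81 / (1 − 0.10) = 90. This reproduces. The protocol does not quantify the effect of LOCF, so that has to be worked out.

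**Inputs**

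- n = 90 per arm and an 8-point margin, read as an absolute difference (II.3.3 (2)).
- One-sided 0.025. II.3.3 (2) gives α = 0.05 without a side; II.7 (2) ① makes tests other than superiority two-sided. One-sided 0.05 is shown as a variant.
- Dexamethasone RIOM rate 80% (I.1 says over 80%), with 68.75% from the retrospective series (section VIII) as the lower case.
- d, the share lost before onset, is assumed. The 10% in II.3.3 (2) is overall loss, and follow-up runs 3 months (II.3.6) or 12 months (III.4).

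**Formula.** If leavers have the same RIOM risk as the others, the recorded rate under LOCF is p(1 − d). Non-inferiority is declared when the upper Wald limit of Sapylin minus dexamethasone is below 0.08. The probability is summed exactly over both binomial distributions.

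**Sapylin truly at the margin (88% vs 80%): chance of falsely declaring non-inferiority**

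| Early loss, Sapylin / dexamethasone | Recorded rates | Recorded difference | One-sided 0.025 | One-sided 0.05 |
|---|---|---|---|---|
| 0 / 0% | 88.0 / 80.0% | 8.0 | 2.7% | 5.3% |
| 2 / 2% | 86.2 / 78.4% | 7.8 | 2.9% | 5.6% |
| 5 / 5% | 83.6 / 76.0% | 7.6 | 3.2% | 6.0% |
| 10 / 10% | 79.2 / 72.0% | 7.2 | 3.5% | 6.7% |
| 4 / 2% | 84.5 / 78.4% | 6.1 | 5.6% | 9.9% |
| 2 / 4% | 86.2 / 76.8% | 9.4 | 1.5% | 3.1% |
| 12 / 8% | 77.4 / 73.6% | 3.8 | 9.8% | 16.4% |
| 8 / 12% | 81.0 / 70.4% | 10.6 | 1.0% | 2.1% |

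For 4 / 2%: 0.88 × 0.96 = 0.8448, 0.80 × 0.98 = 0.784, difference 0.0608. In patients, 0.04 × 90 = 3.6 against 0.02 × 90 = 1.8, so about four against two. Balanced 10% and the last two rows place the whole loss allowance before onset and are stress cases; balanced 5% places half of it there.

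**Lower control rate (76.75% vs 68.75%).** No loss 2.6%; 4 / 2% gives 4.5%; 12 / 8% gives 7.5%.

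**Leavers at different risk.** Let leavers have k times the risk of the others, with the true overall rates held at 88% and 80%. The recorded rate is p(1 − d) / ((1 − d) + kd).

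- k = 0.5: 4 / 2% gives 0.8448 / 0.98 = 0.862 against 0.784 / 0.99 = 0.792, and 4.0%; 2 / 4% gives 2.0%.
- k = 0: Grade 0 is correct for every leaver and the result stays at 2.7%.
- Every leaver would have had RIOM (recorded rate p − d): 4 / 2% gives 5.7% and 2 / 4% gives 1.2%.

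**Sapylin equal or better, balanced loss: chance of declaring non-inferiority**

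- 80% in both arms: 27.7% with no loss, then 26.3%, 24.6% and 22.5% at 2, 5 and 10%.
- Retrospective rates (43.75% vs 68.75%): at 10% loss the benefit shrinks from 25.0 points to 25.0 × 0.90 = 22.5, and the chance from 99.5% to 98.7%.

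**Scale of the shift.** With equal true rates the shift is p × (difference in d). A full 8-point shift needs a gap in early loss of 0.08 / 0.80 = 10 points, or 0.08 / 0.6875 = 11.6 points.

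**Does the remedy work?** A simulation at 88% vs 80% (4,000 runs, 20 imputations, assumed onset on days 10 to 35 and loss on days 1 to 20) gave these false non-inferiority rates, LOCF then multiple imputation: 4 / 2%, 4.6% then 2.6%; 2 / 4%, 1.7% then 3.0%; 12 / 8%, 8.7% then 2.8%; 2 / 2%, 2.9% then 3.1%. Monte Carlo error is about 0.26 points, since √(0.027 × 0.973 / 4000) = 0.0026. The onset and loss days are not from the protocol, so this is indicative only.

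**The case against.** The best case for leaving the rule alone is that loss before onset will be rare. Patients attend 33 fractions, five a week, and are graded at daily rounds. A patient who stops the nebuliser but continues radiotherapy can still be graded, and dropouts are to be assessed as far as feasible. Much of the 10% allowance may fall in follow-up after treatment, which cannot change incidence. At balanced 2% the error is 0.2 points, and imputation gains nothing measurable there. This stands, and it is why the point is not graded higher. It does not cover a small imbalance: about four early leavers against two roughly doubles the false non-inferiority rate at 80%.

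Perceived ineffectiveness is also a weak reason for loss before onset, since a patient with normal mucosa has little cause to think the treatment is failing. That is fair. Intolerable reactions remain as a reason, with nothing in the protocol on how often either drug would cause early withdrawal. The section VIII series reports no obvious toxicity with Sapylin, but it has only 16 patients per arm.

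The 80% control rate is on the high side of the protocol's figures. At 68.75% the effect is smaller (4.5% rather than 5.6%) but of the same kind.

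The PPS requires measurable primary variables, so it probably drops these patients. That limits the harm, but it does not test the LOCF assumption or correct the FAS result, and the protocol does not require both sets to succeed.

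Imputation detail is commonly left to an analysis plan. Here, though, the protocol has already chosen the method, and the choice is unsuitable. The severity definition, the two-set success rule and the exclusion criteria are separable and could be settled on their own.

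**Conclusion.** The concern holds. LOCF, as prescribed, gives a wrong value for most patients lost before onset if their RIOM risk is near the background rate. With balanced early loss the effect is small: 2.7% to 2.9% false non-inferiority at 2% loss, 3.5% at 10%, and a modest loss of power if the drugs are equal. With unequal loss it can favour either drug: 5.6% at 4 / 2% and 1.5% at 2 / 4%, or 4.0% and 2.0% if leavers have half the others' risk. There is no bias if leavers would never have developed RIOM.

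These sizes rest on n = 90, an absolute 8-point margin, one-sided 0.025, an 80% control rate and assumed early loss. Confidence is medium because the protocol gives neither the timing of loss nor its split by arm. The rule should be changed before the data are examined, but it does not by itself undermine the trial.

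**What to change.** In II.7 (2) ②, delete LOCF for RIOM and put in its place:

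- Multiple imputation of RIOM status and worst grade, within arm. For a patient who leaves on a given day, draw from same-arm patients still under observation who had the same grade on that day, using the grades recorded at daily rounds. State that this targets the outcome had the patient continued chemoradiotherapy.
- A tipping-point analysis that varies the RIOM rate among early leavers separately in each arm, to show what rates would overturn the conclusion.

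Three related clarifications belong with it:

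- Define severity as the worst WHO grade from the start to the end of chemoradiotherapy.
- Say that non-inferiority is claimed only if the FAS and the PPS both meet the margin.
- Say which analysis set III.3.4 ③ and ④ govern, so that they no longer conflict with the FAS definition.

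The cost is protocol wording and some extra analysis of grades already collected. The interval widens slightly: at 80% in both arms the 95% half-width goes from 1.96 × √(2 × 0.16 / 90) = 11.7 points to at most about 1.96 × √(2 × 0.16 / 81) = 12.3 points, if 10% of the information is lost.

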# **Efficacy and Safety of Sapylin Versus Dexamethasone Atomized Inhalation for Concurrent Chemoradiotherapy-Induced Oral Mucositis in Patients With Nasopharyngeal Carcinoma: A Randomized, Parallel, Non-inferiority Clinical Trial**

## **I. Rationale**

### **1. Background**

Nasopharyngeal carcinoma (NPC), an epithelial malignancy originating from the nasopharyngeal mucosa, is one of the common head and neck malignancies. Globally, 70% of new cases occur in East and Southeast Asia. Nearly 80% of global patients are concentrated in China, leading to its nickname, "China Cancer". Within China, it is highly prevalent in the southern regions, especially the Guangdong, Guangxi areas and Hong Kong, hence the common name "Guangdong Cancer". Currently, radiotherapy is the primary treatment modality for NPC. Seventy percent of patients are diagnosed at an advanced stage. For Locally Advanced NPC (LA-NPC), induction chemotherapy combined with Concurrent Chemoradiotherapy (CCRT) is the standard treatment regimen. Since the adoption of induction chemotherapy combined with CCRT for LA-NPC patients, overall survival rates have improved. However, over 20% of LA-NPC patients still experience treatment failure and have a 5-year survival rate lower than 5 years. Furthermore, during radiotherapy, the radiation causes varying degrees of damage to the normal tissues adjacent to the tumor. Adverse reactions such as dry mouth and radiation-induced oral mucositis can reduce patient compliance. In severe cases, these can lead to clinical adverse outcomes such as reduced radiation dosage, treatment interruption, prolonged hospitalization, or even life-threatening situations, thereby negatively impacting the efficacy and quality of life associated with CCRT. The INT0099 trial showed that 37% of patients receiving CCRT terminated treatment prematurely due to excessive toxicity.

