## **3. Research Protocol**

### **3.1 Study Design Type**

Non-inferiority, parallel-design, randomized controlled clinical study.

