### **3.5 Clinical Treatment Protocol**

#### (1) Experimental Group

Concurrent Radiotherapy Dose: Nasopharyngeal primary tumor site (PTVnx): 69.96Gy/2.12Gy/33F; High-risk planning target volume (PTV1): 60.06Gy/1.82Gy/33F; Low-risk

planning target volume (PTV2): 54.12Gy/1.64Gy/33F; Cervical lymph nodes (PTVnd): 66~69.96Gy/2~2.12Gy/33F; 5 times per week, for a total of 6-7 weeks.

Concurrent Chemotherapy: Cisplatin (80-100 mg/m^2, Q3W, 3 times during CCRT); Sapylin: 1 KE/time, nebulized, QD, starting from Day 1 of CCRT until the end of radiotherapy.

(2) Control Group:

Concurrent Radiotherapy Dose: Nasopharyngeal primary tumor site (PTVnx): 69.96Gy/2.12Gy/33F; High-risk planning target volume (PTV1): 60.06Gy/1.82Gy/33F; Low-risk planning target volume (PTV2): 54.12Gy/1.64Gy/33F; Cervical lymph nodes (PTVnd): 66~69.96Gy/2~2.12Gy/33F; 5 times per week, for a total of 6-7 weeks.

Concurrent Chemotherapy: Cisplatin (80-100mg/m^2, Q3W, 3 times during CCRT); Dexamethasone: 10mg/time, nebulized, QD, starting from Day 1 of treatment until the end of radiotherapy.

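### The whole-course 80–120% drug-use rule can drop patients from the Per Protocol Set after their RIOM event, so for RIOM incidence PPS membership can depend on the primary outcome

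*Protocol*

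**What the plan says.** Section 3.1 of the protocol describes the trial as a "Non-inferiority, parallel-design, randomized controlled clinical study". Section 6 gives the endpoint: "Primary Evaluation Indicator: Incidence and severity of RIOM".

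Under Statistical Analysis Populations (section 7(2)②), PPS patients must, among other conditions, "have good compliance (used the trial drug quantity between 80% and 120" per cent). The same section says: "Primary efficacy endpoints will be analyzed simultaneously on the FAS and PPS". It does not say which set governs or whether both must succeed. The Full Analysis Set (FAS) takes every randomised patient with at least one treatment and fills incomplete courses by last observation carried forward.

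Section 3.5 gives the Sapylin schedule as "nebulized, QD, starting from Day 1 of CCRT until the end of radiotherapy"; the dexamethasone schedule also ends with radiotherapy. Section 3.2(1) has RIOM graded on daily rounds during this course and adds: "The incidence and severity of RIOM will be statistically analyzed after the completion of concurrent chemoradiotherapy".

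The Background (section I.1) states: "Adverse reactions such as dry mouth and radiation-induced oral mucositis can reduce patient compliance".

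**The concern.** Incidence is settled on the day RIOM first appears. If a patient has taken every dose to that day, the event was observed under full exposure, and nothing that happens to the nebuliser afterwards changes it. A rule that counts drug use to the end of radiotherapy nevertheless lets later under-use remove both patient and event from the PPS.

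If RIOM itself makes stopping more likely, exclusion depends on the endpoint. If it does so more in one arm than in the other, the PPS difference is biased. In a non-inferiority trial the PPS is normally included to guard against dilution of a real difference, so a PPS partly selected on outcome is a weak guard. The bias can make an inferior result look acceptable or make an acceptable result fail, depending on which arm stops more.

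**Working it through.** **Does the rule reach past the event?** Radiotherapy is 33 fractions over 6–7 weeks (section 3.5).

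- One dose per fraction: 0.80 × 33 = 26.4, so at least 27 doses are needed.
- One dose per calendar day: 0.80 × 42 = 33.6 and 0.80 × 49 = 39.2, so 34 to 40 doses are needed.
- A patient who takes every dose, develops RIOM and stops on day 21 of an assumed 45-day course has used 21/45 = 47% (50% of 42 days, 43% of 49). That patient leaves the PPS with the event.
- A patient who stops after the threshold stays in.

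**How far can the PPS difference move?** The protocol gives no compliance or stopping figure to reproduce.

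From the protocol: 90 per arm, a margin of 8% (taken as 8 percentage points) and α = 0.05.

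Assumed: true RIOM p = 80% on dexamethasone and 88% on Sapylin, exactly at the margin; a fraction f of RIOM patients failing the 80% rule, varied by arm; a fraction g = 5% of RIOM-free patients failing it; and a one-sided 95% upper bound with Wald variance.

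- PPS rate = p(1−f) / [p(1−f) + (1−p)(1−g)]
- PPS size = 90 × [p(1−f) + (1−p)(1−g)]

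Worked case, f = 20% dexamethasone and 40% Sapylin:

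- Dexamethasone: 0.80×0.80 = 0.640; 0.20×0.95 = 0.190; rate 0.640/0.830 = 77.1%; n = 74.7.
- Sapylin: 0.88×0.60 = 0.528; 0.12×0.95 = 0.114; rate 0.528/0.642 = 82.2%; n = 57.8.
- Difference d = 5.1 points; SE = √(0.771×0.229/74.7 + 0.822×0.178/57.8) = 0.070.
- P(non-inferiority) ≈ Φ((0.080 − 0.051)/0.070 − 1.645) ≈ 11%. Simulation agrees.

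The same steps for other stopping fractions, with probabilities from simulation:

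| f dexamethasone / Sapylin | PPS difference (true 8.0) | False non-inferiority, PPS alone |
|---|---|---|
| 20% / 40% | 5.1 points | about 11% |
| 20% / 50% | 2.3 points | about 18% |
| 10% / 15% | 7.7 points | 5.9% |
| 20% / 20% | 9.0 points | 3.9% |
| 30% / 15% | 12.1 points | 1.3% |

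**With the FAS alongside.** The FAS alone gives 5.3% in this set-up. If both sets must succeed, false non-inferiority is 5.0% at 20%/40% and 5.3% at 20%/50%. The opposite imbalance then costs power: with equal true RIOM of 80% and 30%/15% stopping, success falls from 39% on the FAS alone to 16% on both.

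**At the pilot rate.** Take 68.75% on dexamethasone (section VIII) and 76.75% on Sapylin, one-sided 2.5%, g = 0. With 10% of RIOM patients stopping on dexamethasone and 20%, 30% or 40% on Sapylin, the 8-point excess becomes 6.1, 3.4 or 0.0 points. PPS-alone false non-inferiority is 4.5%, 8.9% or 17.2%. Equal stopping of 20% gives 8.8 points and 2.0%.

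**Does stopping the count at first RIOM help?** A day-level simulation assumed a 45-day course, RIOM onset uniform on days 10–35, unrelated stopping of 5% or 15% by 80% of the course, and RIOM-related stopping of 15–50% by arm. The written rule gave differences of 3.3 to 12.0 points against a true 8. Counting compliance only to first RIOM gave 7.5 to 7.9.

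**The case against.** **The FAS protects.** A reader might infer that a truly inferior Sapylin could pass because of this rule. That needs the PPS to decide alone, and the protocol does not say it does. The FAS retains these patients, and requiring both sets removes the inflation. This stands, but the protocol does not require both, and the requirement leaves the loss of power under the opposite imbalance.

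**RIOM has not been shown to stop nebulising.** The Background sentence concerns compliance in general and goes on to radiotherapy dose and interruption. The same section credits nebulised therapy with better compliance, and section VIII describes the drugs as for treatment as well as prevention, so affected patients may have reason to continue. This stands: the documents make the link plausible and do not establish it.

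**The bias favours Sapylin.** The documents do not support this reading. Direction depends on which arm stops more, and equal stopping makes the PPS slightly conservative in these examples.

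**The denominator is not written out.** If it means the quantity due until radiotherapy actually ends, a patient whose radiotherapy is cut short may count as fully compliant, and the problem shrinks. Whole course is the natural reading, not a stated one.

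**Severity is also primary.** It evolves after onset, so later dosing is relevant adherence there. This stands and limits both the point and the remedy to incidence.

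**RIOM-free patients can also leave the PPS**, through other adverse events or withdrawal. True; they lack only the route that runs through RIOM.

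**Compliance is already compared by arm** (section 7(2)③C.b). It is not broken down by RIOM status, so that table would not show this selection.

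**Conclusion.** The point holds for RIOM incidence. On the natural reading of the compliance rule, the PPS can exclude patients for under-use that comes after an observed primary event, so membership can depend on the outcome in a set on which the primary endpoint is analysed.

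The magnitude cannot be fixed from the documents. RIOM rates at the margin and all stopping fractions are assumed, and the one-sided 5% level is a choice, since the general principles prescribe two-sided tests outside superiority. Over the stopping patterns tabulated, a true 8-point difference appears in the PPS as anything from 2.3 to 12.1 points. A modest imbalance (10%/15%) barely matters. The larger error rates belong to the PPS read alone and should not be taken as the trial's error rate.

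The change should be made because it is cheap and uses data already recorded. It does not show the planned analysis to be invalid.

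**What to change.** In the PPS definition:

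1. For the analysis of RIOM incidence, judge the 80–120% rule from Day 1 to the first RIOM of any grade, or to the end of radiotherapy if there is none. Do not exclude a patient with observed RIOM for later under-use.
2. For the analysis of severity, keep the whole-course rule, and show the result with and without patients excluded for under-use after onset.
3. State that non-inferiority on incidence requires success on both FAS and PPS.
4. Tabulate PPS exclusions by arm and RIOM status.

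This should be settled before PPS membership is decided. It costs a few sentences and uses the daily RIOM records and dosing data already planned; no treatment or assessment changes. The downsides are two PPS definitions to maintain and a small residual bias, about 0.5 point at most in the simulation, because patients with early RIOM have a shorter window in which to be judged non-compliant. Requiring both sets also makes success harder if the PPS is noisier than the FAS.
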